C.1.3. Endotoxin induces changes in KYN metabolism, which correlates with depressed mood

[figure not shown]

Fig. 5 Leucine reduces brain KYN:TRP ratios and blocks depression-like behavior. **A,B** Mean sucrose preference (%) and time spent immobile in the forced swim test (s) (\pm SEM) of mice treated with leucine or vehicle immediately before and 6 h after LPS or phosphate-buffered saline (PBS) ($n > 14$ per group). **C,D** Mean KYN:TRP ratios in plasma and brains (\pm 442 SEM) of mice treated with 50 mg/kg leucine or vehicle immediately before and 6 h after LPS or PBS ($n = 5$ per group).

** $p < 0.01$, *** $p < 0.001$ for LPS vs. PBS main effects. * $p < 0.05$, ** $p < 0.01$, *** $p < 0.001$ for leucine vs. vehicle main effects.

Aim: In the aforementioned study in C.1.2. (N=115), we examined whether endotoxin induces changes in kynurenine metabolism and whether these changes correlate with inflammation-induced depressed mood.

Methods: Circulating kynurenine metabolites (TRP, KYN, QA, KynA) were measured at T₀, T₂, and T₆. The primary outcome was IDO activity assessed using KYN/TRP. **Results:** Participants exposed to endotoxin (vs. placebo) showed greater increases in IDO activity (p<0.0001). Among endotoxin-exposed participants (N=61; 38 females), the correlation between IDO activity and depressed mood was highly significant (p=0.004).

Conclusion: Inflammatory challenge increased IDO activity, which in turn was significantly correlated with inflammation-induced depressed mood. *These data confirm endotoxin-induced increases in peripheral conversion of TRP to KYN as well as increases in depressed mood, and thus show the feasibility of inhibiting blood-to-brain transport of KYN as well as inflammation-induced depressed mood.*

C.2. Research Design and Methods

C.2.1. Overview of Study Design (Fig. 6):

In this double-blind randomized placebo-controlled four-arm study, a total of 90 healthy volunteers (ages 18-65) will be randomly assigned to a two-week pretreatment of L-leucine (hereafter referred to as leucine) or PO placebo (i.e., maltodextrin). After the pre-treatment period, they will receive low-dose endotoxin or IV placebo (i.e. saline): n₁=35 leucine + endotoxin; n₂=35 PO placebo + endotoxin; n₃=10 leucine + IV placebo; n₄=10 PO placebo + IV placebo. (see Justification of Sample Size for the rationale for smaller IV placebo arms)

[figure not shown]

Fig. 6 Overview of study design

C.2.2. Subjects:

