Endotoxin Administration (Main Study Session): The main study session including endotoxin administration and experimental tasks will be conducted at the UCLA Clinical & Translational Research Center (CTRC). Participants will arrive at the CTRC at 07:00. Upon arrival, a urine sample will be collected and tested for drug use and pregnancy in order to ensure continued eligibility for study participation. A CTRC nurse will assess vital signs (blood pressure, pulse, temperature). An indwelling venous catheter with a heparin lock will be inserted into the participant's dominant forearm for hourly blood draws and one into the non-dominant forearm for endotoxin administration. Oral hydration with water or juice will be offered hourly in order to minimize the negative side effects of endotoxin (hydration reduces risk of diastolic blood pressure decreases). Following these procedures, participants will eat a light breakfast before undergoing experimental tasks and taking the last dose of study drug at 08:30. At 09:00 (T_0), participants will receive endotoxin (0.8 ng/kg of body weight) or IV placebo as an intravenous bolus over 30-60 seconds. Endotoxin to be used in this study is derived from *Escherichia coli* (*E. coli* group O:113) and will be provided by the NIH Clinical Center.⁹¹

Safety Monitoring and Discharge from Study: Participants will be monitored as per the protocol (see Protections of Human Subjects section) and discharged following the last blood draw upon approval from the study physician. Briefly, in addition to the continuous observation, scheduled nursing assessments including vital sign check will be performed every 30 minutes for the first 2 hours after LPS administration and then hourly. If any potential adverse reactions are noted as detailed in the protocol, the study physician will be contacted and the pre-determined actions will be taken as appropriate such as ECG, verbal or manual stimulation, relieving medications, or discontinuation of the study procedures.

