The basic design is a 2 group (leucine vs. PO placebo) by 2 condition (endotoxin vs. IV placebo) independent analysis of variance (ANOVA) with one or more repeated outcome measures analyzed with linear mixed models (LMM) with primary focus upon the two endotoxin-exposed groups. The number of repeated measures varies by assessment. The key results are the main effects of pretreatment (i.e., group) while the main effects of group, condition, and their interaction will be tested. For analyses with repeated measures, the two main effects and interaction will further interact with the time variable. POMS will be the primary outcome measure. Simes correction for multiple testing will be applied for the secondary outcome measures as they are expected to be correlated.¹¹⁰

C.2.9. Justification of Sample Size

The effect sizes for the reduction of endotoxin-induced depressive symptoms by leucine within the animal data are very large ($d=.90$), but we have assumed some attenuation in humans ($d=.70$). Assuming an effect of this size, with $n=35$ per group, there is >80% power to detect differences between the leucine and PO placebo pretreatments with endotoxin exposure for the single time point outcomes (e.g., Cyberball Social Exclusion); comparisons for repeated measures assessments will have more power (>90%) and able to detect more subtle effects at >80% power. Both 'leucine + IV placebo' and 'PO placebo + IV placebo' arms are expected to show minimal depression with means over time to be very near zero but exist as reference points to the endotoxin condition, which our previous work suggests to have large effects. With repeated measures, $n=10$ can detect

medium sized effects ($d=.50$) with power $>80\%$. Thus, there is more than adequate power with 35 vs. 10 to show the effect of endotoxin exposure within pretreatment groups.

REFERENCES

3. Depression Guideline Panel: Clinical Practice Guideline 5: Depression in Primary Care, vol 2: Treatment of Major Depression. In: US Department of Health and Human Services PHS, Agency for Health Care Policy and Research, ed. Rockville, MD. 1993.

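### The >80% power that C.2.9 gives for single-time-point outcomes leaves out the Simes correction in C.2.8 and any loss of participants; corrected power is about 65-79% across the four affect outcomes

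*Combined protocol and SAP*

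**What the plan says.** C.2.8 (Statistical Analysis) names a single primary outcome: "POMS will be the primary outcome measure". It then sets the multiplicity rule: "Simes correction for multiple testing will be applied for the secondary outcome measures as they are expected to be correlated". It does not say which outcomes form the family, or whether Simes is meant as a global test, as step-up cut-offs or as a closed procedure.

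C.2.9 (Justification of Sample Size) takes a standardised difference of 0.70, reduced from 0.90 in the animal data, and 35 per group. It concludes that "there is >80% power to detect differences between the leucine and PO placebo pretreatments with endotoxin exposure for the single time point outcomes", with Cyberball as the example. The significance level, sidedness, correction and attrition are not mentioned there.

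The Specific Aims place social rejection, which Cyberball measures, among the four affect outcomes of Aim 2. C.2.6 says that Cyberball and the Positive Social Feedback task are each done once.

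On numbers, C.2.1 says "a total of 90 healthy volunteers (ages 18-65) will be randomly assigned to a two-week pretreatment", with 35 in each endotoxin arm. C.2.3 has participants dose at home for two weeks; on the session morning their urine is "tested for drug use and pregnancy in order to ensure continued eligibility for study participation".

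**The concern.** The outcome chosen to illustrate adequate power is one that the preceding section says will be tested under a multiplicity correction. The power quoted is therefore not the power of the planned test. It also uses the randomised number as if all 35 per arm will be evaluable, although there is a two-week interval and a repeat eligibility check before the outcome is measured.

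Aims 2 and 3 rest on secondary outcomes, and A.6 and C.2.7 rely on the affect tasks to separate mood effects from sickness symptoms. If a corrected Cyberball comparison is null, a reader who trusts the stated power could take it as firmer evidence of no effect than the design can give. The primary POMS comparison is not affected.

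**Working it through.** **Inputs.** Standardised difference d = 0.70 and 35 per arm (C.2.9). One primary outcome and Simes for the secondary outcomes (C.2.8). Four affect outcomes (Specific Aims) and five cognitive tests (C.2.5). Two tasks measured once (C.2.6). Assumed, because the plan is silent: two-sided 0.05, family size m, correlation 0.3 between outcomes, number of outcomes that truly respond (each at d = 0.70, the rest at zero), and losses.

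**Step 1: the plan's own figure.** Noncentrality = d × √[n₁n₂/(n₁+n₂)] = 0.70 × √(1225/70) = 0.70 × 4.183 = 2.928. With 68 degrees of freedom the two-sided 0.05 critical value is 1.995, and power is **82.3%** (83.4% by the normal approximation). The claim of more than 80% reproduces without correction.

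**Step 2: losses, still uncorrected (exact t).**

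| Evaluable per arm | Total lost | Power |
|---|---|---|
| 34 / 34 | 2 | 81.2% |
| 34 / 33 | 3 | 80.6% |
| 35 / 32 | 3 | 80.5% |
| 33 / 33 | 4 | 80.0% (79.97%) |
| 32 / 32 | 6 | 78.7% |

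**Step 3: correction, 35 per arm.** With step-up Simes cut-offs, order the p-values, find the largest i with p₍ᵢ₎ ≤ 0.05 × i/m, and claim every outcome with a p-value up to p₍ᵢ₎.

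If only Cyberball responds, the test level is close to 0.05/m. The exact t then gives 73.7% for m = 2 (level 0.025), 64.2% for m = 4 (0.0125) and 52.9% for m = 9 (0.0056). Simulation is slightly higher, because a chance small p-value elsewhere can relax the cut-off. If every outcome responds, the cut-off moves towards 0.05, and power approaches 82.3% without reaching it.

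Simulated t-tests (correlation 0.3, 40,000 runs) give this power for one outcome:

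| Family | Only it responds | All respond |
|---|---|---|
| Two once-measured tasks | 74% | 80% |
| Four affect outcomes | 65% | 79% |
| Nine (four affect, five cognitive) | 54% | 78% |

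Intermediate cases: 71% for the family of four if two respond, and about 67% for the family of nine if four respond. Hochberg (cut-offs 0.05/(m−i+1)) gives 64% to 76% for the four affect outcomes.

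**Step 4: both together.** At an assumed 32 per arm, step-up power is about 60% to 74% for the family of four and about 48% to 73% for the family of nine.

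**Step 5: error rate if step-up cut-offs are used for individual claims.** The chance of at least one false claim is about 4-6% for four outcomes with one to three real (correlation 0.3). For nine pooled outcomes with four real it is about 10%, 9%, 7% and 5% at correlations of 0, 0.3, 0.6 and 0.8. Hochberg stays below 4% in the nine-outcome case.

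**The case against.** The strongest reply is that C.2.9 contains no arithmetic error: more than 80% is right for one comparison at 0.05 with 35 per arm. That stands. What is missing is the statement that the figure is per comparison and for complete data.

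Second, the plan fixes no family, correlation, number of real effects or attrition rate, so no single corrected power follows from it. This also stands. The family of nine is an assumption: Aim 3 names four cognitive domains where C.2.5 lists five tests, and C.2.5 has further scales that could be counted. So is 32 per arm. C.2.2 plans regular telephone contact for retention, and the session-morning check shows only that loss is possible. Reporting a range answers this; omitting the correction does not.

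Third, the level might be one-sided. At a one-sided 0.05, uncorrected power is 89.5%, and a family of two gives at least about 82%. With four outcomes of which one responds, it is still only about 74%.

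Fourth, Simes might be meant only as a global test. The chance of rejecting the global null can exceed 90% when several outcomes respond, but that supports no claim about Cyberball itself.

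A reader might also infer that the plan doubles the false-claim rate. The documents do not support that. Rates near 10% need nine pooled outcomes, four real effects and low correlation, while C.2.8 expects correlated outcomes. They also need step-up cut-offs to be used for individual claims, which C.2.8 does not say; a closed procedure is an equally open reading.

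**Conclusion.** The point holds as one of incomplete disclosure. The stated power is an uncorrected, complete-data figure for outcomes that the plan will test with correction. At 35 per arm and two-sided 0.05, corrected power is about 65-79% for the four affect outcomes and about 54-78% for an assumed nine. It just reaches 80% in the most favourable case examined: a family of two, both responding, nobody lost. These ranges rest on step-up cut-offs, correlation 0.3 and d = 0.70 for each responding outcome.

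Two stronger readings should be avoided. One is that any loss breaks the claim: without correction, up to three losses in total still leave more than 80%, and the shortfall at 32 per arm is little more than one point. The other is that 80% is out of reach under Simes: the family of two shows otherwise. The error-rate results are a reason to name the procedure, not a finding that the plan inflates error.

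**What to change.** In C.2.9, state the significance level and sidedness, and replace the claim with wording such as:

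> For a single-time-point outcome at d = 0.70, power is 82% at an uncorrected two-sided 0.05 with 35 evaluable per arm (79% with 32). After step-up Simes correction across the four affect outcomes it is about 65-79%, depending on how many respond (correlation 0.3 assumed).

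In C.2.8, list the outcomes in each family and name the procedure that supports individual claims. One option is Hochberg or Hommel within each aim; Hochberg gives about 64-76% for the four affect outcomes, and that range should then replace the 65-79% above. The other is false-discovery-rate control, with claims worded to match.

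The cost is a few sentences and a line of analysis code, with no change to design or sample size. The downside is a less favourable stated power; Hochberg or Hommel is also somewhat more conservative per outcome than step-up Simes cut-offs.

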Behavioral Measures: Depressed mood, a core symptom of depression, will be assessed immediately before endotoxin administration (T_0) and then hourly for the next 6 hours (T_1-T_6) using the POMS⁶⁷ (primary outcome). We will also use the MADRS⁹⁷ hourly (T_0-T_6) as it is sensitive to acute changes in depressed mood and anhedonia following endotoxin¹⁹ and is less oriented towards somatic symptoms than the Hamilton Depression Rating Scale. Because feelings of social disconnection and loneliness predict depression and co-occur with depressed mood following inflammatory challenge, feelings of social disconnection (Feelings of Social Disconnection Scale²¹) and loneliness (adapted UCLA Loneliness Scale⁹⁸) will also be assessed.

Participants will also complete self-report measures of sickness symptoms (e.g., muscle pain, fatigue).

Cognitive Measures: Three items from the POMS-Confusion subscale (unable to concentrate, forgetful, confused) will be assessed at T_0 and then hourly (T_1-T_6).⁶⁷ Verbal memory, visual memory, executive function, and attention be assessed at T_0 and then between T_2 and T_3 using computerized tests from CNS Vital Signs™: Verbal Memory Test, Visual Memory Test, Stroop Test, Shifting Attention Test, and Continuous Performance Test. Reichenberg et al. assessed cognitive impairment at 1, 3, and 9 hours after endotoxin and found it to be worst at 3 hours.²⁰ The order of tests will be counterbalanced across subjects to avoid any non-random version-dependent bias.⁹⁹

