Reward (Reward Learning Task): Anhedonia is a core feature of major depressive disorder and includes a reduction in experienced pleasure (liking reward) and dysfunction in reward anticipation reward learning.⁷⁸⁻⁸⁰ We have found that inflammatory challenge reduces neural sensitivity to reward anticipation.¹⁰⁸ We will use a laboratory based probabilistic reward task that objectively measures participants' ability to modulate behavior as a function of reward, because this task identifies reduced reward learning in depressed patients which is state-dependent and also predicts the persistent diagnosis of depression in the midst of treatment.⁷⁸⁻⁸⁰ This computerized reward-learning task is extensively described in Pizzagalli et al.¹⁰⁹

Order and Timing of Experimental Tasks: The order of the tasks will be first a randomized sequence of Reward Learning and Emotional Face Recognition, then followed by a randomized sequence of Positive Social Feedback and Cyberball Social Exclusion. Because the latter two tasks involve deception, they will be completed only once after the former two tasks, at T₂, time of peak cytokine responses. The former two tasks will be completed at T₀ and T₂.

C.2.7. Interpretation of Results and Potential Pitfalls

As leucine may not inhibit endotoxin-induced inflammation, unopposed sickness symptoms could mask the antidepressant effects of leucine assessed using the POMS. Thus, the results will be statistically adjusted for sickness symptoms. Furthermore, we will use experimental tasks of negative and positive affect to assess mood-specific processes. Although the proposed leucine dose is above average,^{30,87} the adequate antidepressant dose is unknown. Thus, if an interim data analysis for the first 30 participants using 12 g/day shows no signal of an antidepressant effect, we will consider increasing the dose to 16 g/day for the same period of 14 days. Of note, 16 g/day was the maximum dose of leucine used in long-term supplementation studies according to a meta-analysis.³⁰

C.2.8. Statistical Analysis

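### For outcomes measured in the main session only at T0 and about T2, the named key test (pretreatment main effect) has roughly 33–46% power under stated assumptions, not the >90% claimed for repeated measures

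*Combined protocol and SAP*

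**What the plan says.** C.2.9 takes d=.90 from the animal data and then says "we have assumed some attenuation in humans ($d=.70"). For outcomes taken once, it says that "with $n=35$ per group, there is >80% power to detect differences between the leucine and PO placebo pretreatments with endotoxin exposure". For outcomes taken more than once, it says "comparisons for repeated measures assessments will have more power (>90" percent). It gives no alpha, within-person correlation, number of occasions or model term for either figure.

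C.2.8 describes linear mixed models "with primary focus upon the two endotoxin-exposed groups" and names the test of interest: "The key results are the main effects of pretreatment (i.e., group"). It adds: "For analyses with repeated measures, the two main effects and interaction will further interact with the time variable". Nothing in C.2.8 makes T0 a covariate or confines the main effect to values taken after endotoxin.

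On timing:

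- Reward Learning and Emotional Face Recognition (C.2.6, order and timing of tasks): "The former two tasks will be completed at" T0 and T2.
- CNS Vital Signs tests (C.2.5, Cognitive Measures): "Verbal memory, visual memory, executive function, and attention be assessed at" T0 and then between T2 and T3. C.2.4 lists the same five tests at in-person screening, before study drug.
- POMS, the primary outcome (C.2.5, Behavioral Measures): T0 and then hourly from T1 to T6, with a screening value as well (C.2.4).

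C.2.5 places the T0 mood assessment immediately before endotoxin, and C.2.3 puts the bolus at T0, after the pre-injection tasks and the last dose of study drug.

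**The concern.** Extra occasions raise the power of a main effect only if the treatment difference is present at each of them. The aims concern responses to endotoxin, and at T0 there has been none. For an outcome with one value before and one after, the main effect is the average of a zero and the full difference. The signal halves, while the noise falls only by the factor √((1+ρ)/2). The plan's statement that repeated measures have more power is then reversed for these outcomes.

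The outcomes affected are two of the four Aim 2 tasks and the whole computerized battery of Aim 3. A null main effect on them would be read as coming from a test with more than 90% power, and so as evidence against leucine, when the test had well under an even chance of detecting the effect the plan assumes.

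**Working it through.** **Inputs from the plan.** 35 per endotoxin-exposed arm and d=.70 (C.2.9); the comparison of the two endotoxin arms and the main effect as key result (C.2.8); the timings above.

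**Inputs assumed, because the plan does not give them.** Two-sided α=0.05; equal correlation ρ between any two occasions, shown over a range; equal variances; no dropout; no group difference at T0. All results are before the Simes correction that C.2.8 applies to secondary outcomes.

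**Method.** Two-sample noncentral t with 68 df and noncentrality d_eff × √(35·35/70) = d_eff × 4.183.

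**Step 1: the plan's own figures.** For a single value, d_eff=.70 and the noncentrality is 2.93, giving power of 82.3%. The stated >80% is reproduced. For two occasions with the full .70 at *both*, d_eff = .70/√((1+ρ)/2), and power is 94.7%, 91.5%, 89.7% and 86.1% at ρ = .3, .5, .6 and .8. With two occasions, then, >90% is reproduced only if the whole difference already exists at T0 and ρ is about .5 or less.

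**Step 2: two occasions with no difference at T0.** The averaged effect is (0+.70)/2 = .35.

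- Main effect: d_eff = .35/√((1+ρ)/2)
- Main effect with the screening value as covariate (cognitive tests only): d_eff = .35/√((1+ρ)/2 − ρ²)
- Group-by-time (T2 minus T0): d_eff = .70/√(2(1−ρ))
- T2 adjusted for T0: d_eff = .70/√(1−ρ²)

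| ρ | Main effect | Main effect, screening covariate | T2 minus T0 | T2 adjusted for T0 |
|---|---|---|---|---|
| .2 | 46.2% | 48.8% | 62.6% | 83.8% |
| .3 | 43.3% | 48.8% | 68.4% | 85.7% |
| .5 | 38.5% | 53.2% | 82.3% | 91.5% |
| .6 | 36.5% | 58.6% | 89.7% | 95.0% |
| .7 | 34.7% | 67.2% | 96.1% | 98.1% |
| .8 | 33.1% | 80.8% | 99.5% | 99.8% |

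Worked row, ρ=.5: main effect .35/√.75 = .404; with screening covariate .35/√.50 = .495; change .70/√1 = .70; T0-adjusted .70/√.75 = .808.

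At ρ=0 the main effect reaches 53.2%. That is its ceiling without a covariate for any non-negative correlation, and it is below the 82.3% of T2 alone.

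**Step 3: POMS, for contrast.** There are seven occasions. With a constant .70 over T1–T6, the averaged effect is (0+6×.70)/7 = .60 and d_eff = .60/√((1+6ρ)/7). Power is 99.3%, 97.5%, 94.4%, 90.5%, 86.3%, 81.9% and 77.6% at ρ = .2, .3, .4, .5, .6, .7 and .8. One pre-endotoxin value in seven dilutes the effect far less than one in two.

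**The case against.** **The model also contains group-by-time.** This is true, and that term removes the dilution. It passes 90% only above a correlation of about .6, and C.2.8 does not name it as the key result. The stated figure is therefore not secured by it at lower correlations.

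**More than 90% is reachable with the planned data.** This also stands. T2 adjusted for T0 reaches 91.5% at a correlation of .5. But the plan does not specify that analysis, and C.2.9 does not say that its figure refers to it.

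**The cognitive tests have a third value, taken at screening before study drug.** Correct: a reader might infer from the session schedule that they are measured only twice, and C.2.4 shows otherwise. The plan does not say how that value enters the model. As a covariate it lifts the main effect only to about 49–81% over correlations of .2 to .8, still short of 90%.

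**Two weeks of leucine might already have produced a difference at T0.** The zero difference is an assumption. The near-zero expectation in C.2.9 concerns depression in the saline arms, not task or cognitive scores. If half the effect (.35) were present at T0, the averaged effect would be (.35+.70)/2 = .525 and main-effect power about 80% to 63% for correlation .2 to .8. The shortfall shrinks but does not close.

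**A reader might infer that the primary outcome is underpowered too.** The documents do not support that in general. Under a constant effect over T1–T6, POMS keeps >90% up to a correlation of about .5. Nor do they support assuming that the POMS effect fades quickly after T2: they give no time profile, and although C.2.5 puts the peak response at T2, it also justifies later assessments on the ground that depressed mood can persist.

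**Conclusion.** The point holds for the secondary outcomes whose main-session values are only T0 and T2 or T2–T3. For the test that C.2.8 names, power is about 46% to 33% at within-person correlations of .2 to .8, and at most 53% at any non-negative correlation without a covariate. C.2.9 claims >90%, so both the figure and its direction are wrong for these outcomes.

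The exact percentages depend on the assumed alpha, equal correlation and zero difference at T0, and on no baseline covariate. That the main effect falls short of 90% does not depend on where in this range the correlation lies, and it survives screening adjustment of the cognitive tests. Simes correction can only lower these powers.

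For POMS the >90% figure is conditional, not refuted. It holds under a constant post-endotoxin effect with correlation up to about .5, and falls to 86%, 82% and 78% at .6, .7 and .8.

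**What to change.** **In C.2.8**, for Reward Learning, Emotional Face Recognition and the CNS Vital Signs tests, replace the main effect averaged over T0 and T2 as the key result. Use instead the pretreatment comparison at T2 (or T2–T3) adjusted for the T0 value and, for the cognitive tests, also for the screening value taken before study drug. Report the T2-minus-T0 contrast as supporting. It is the weaker choice as key result, because below a correlation of .5 it has less power than a plain T2 comparison. State that T0 follows two weeks of study drug, so that adjusting for it targets the response to endotoxin.

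**In C.2.9**, limit >90% to the outcomes and correlations for which it holds. For the T0/T2 outcomes, give power with alpha and correlation stated: T0-adjusted T2 has about 84%, 86%, 91.5% and 98% at correlations of .2, .3, .5 and .7, before Simes. Give the POMS figure separately, with its assumed correlation and time profile.

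The cost is a change of wording and, at low correlations, a less favourable stated power. No participants, visits or measurements are added.
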